8.6 Follow-up of AEs and SAEs

All AEs and SAEs must be followed until resolution, the condition stabilizes, the event is otherwise explained, or the subject is lost to follow-up. The Investigator is responsible to ensure that follow-up includes any supplemental investigations as may be indicated to elucidate as completely as possible the nature and/or causality of the AE or SAE. This may include additional laboratory tests or investigations, histopathological examinations, or consultation with other health care professionals. ViroMed or their designee may request that the Investigator perform or arrange for the conduct of supplemental measurements and/or evaluations. If a subject dies during participation in the study or

during a recognized follow-up period, a copy of any post-mortem findings will be provided to ViroMed or their designee.

New or updated information will be recorded on the initial SAE Report Form. All corrections to the initial report will be dated and initialed. Each version will need to be sent to the designated CRO via DataFax.

In the event that a subject is lost to follow-up prior to the Investigator's being able to verify that an AE or SAE is resolved, stabilized, or otherwise explained, the site must document in the subject's medical records the repeated attempts (at least 3) to contact the subject and/or his/her care provider to retrieve the information; documentation will include date and mode of communication. In the case of "lost to follow-up." the event is considered as ongoing.

8.7 Immediate Reporting of SAEs

ANY SERIOUS AE THAT OCCURS DURING THIS INVESTIGATION (SEE SECTION 8.2.), WHETHER OR NOT RELATED TO THE STUDY MEDICATION, MUST BE REPORTED IMMEDIATELY TO THE SPONSOR AND/OR THE DESIGNATED CRO.

The reporting timeframes and the required documentation for any SAE occurring during the study are summarized in Table 2.

In the event of an AE leading to hospitalization, every effort will be made by the investigational site to obtain a hospital discharge summary.

In the event of a fatal AE, documentation of any available postmortem findings, including autopsy, will be provided to ViroMed or their designee. In any event, the Investigator will provide a narrative summary of circumstances, events related to the death, and cause of death, if known.

Table 8-1 SAE Reporting Requirements

	Initial Reports	Follow-up Reports
	Fatal/Life Threatening	
Type of SAE	and all other SAEs	Any SAE
Timeframes	24 hours	As additional information become available.
Documents	24 hours: Completed initial SAE Report Form with minimum requirements (subject #, date of birth, event and start date)	Follow-up SAE Report Form and CRF documentation Hospital discharge summary Any relevant diagnostic test results/reports, including pathology reports Any postmortem findings/histopathology results

^a Within 24 hours after the site learns about the event.

NOTE: SAE = Serious Adverse Event.

8.8 Transmission of SAE Reports

DataFax facsimile transmission of the SAE Report is the preferred method to transmit this information. The facsimile information for reporting of SAEs is:

DataFax number: [contact]

Additional information beyond the SAE CRF will be faxed separately to [contact].

8.9 Regulatory Reporting Requirements

The Investigator must promptly report all SAEs in accordance with the procedures detailed in Section 7.3.8. ViroMed has a legal responsibility to notify both the local regulatory authority and other regulatory agencies about the safety of a drug under clinical investigation (21 CFR §312.32).

The Investigator must comply with the applicable local regulatory requirements related to the reporting of SAEs to regulatory authorities and the Institutional Review Board (IRB) or Institutional Ethical Committee (IEC).

This protocol has been filed under an Investigational New Drug (IND) application with the US Food and Drug Administration (FDA). An SAE may qualify as an IND Safety Report (21 CFR §312.32) if the SAE is unexpected, serious, and there is a reasonable possibility that it may have been caused by the investigational drug. In this event, all Investigators filed to the IND (and associated INDs for the same medicinal product) will receive a copy of the IND Safety Report as submitted to the US FDA.

Upon receipt from ViroMed of an initial or follow-up IND Safety Report or other safety information (e.g., revised IDB), the Investigator must promptly notify his or her IRB or IEC.

8.10 Post-Study AEs and SAEs

Investigators are not obligated to actively seek AEs or SAEs beyond the reporting timeframes defined in Section 0. However, if the Investigator learns of any AE or SAEs occurring after the subject's last study visit and the event is deemed by the Investigator to be reasonably possibly related to the use of the study drug, he or she will promptly document and report the event to the safety monitor.

8.11 SAEs Related to Study Participation

An SAE considered related to study participation (e.g., procedures, invasive tests), even if it occurs during the pre- or post-treatment period will be reported promptly to the safety monitor in accordance with the procedures detailed above.

9.0 Statistics

The following sections provide an overview of the planned analysis. A statistical analysis plan (SAP) will be prepared separately from this protocol, which will provide detailed descriptions of the analysis population, statistical methods and models, and tested hypotheses to be analyzed. The SAP will serve as a companion to the protocol and as the *de facto* documentation of the proposed statistical evaluation.

9.1 Sample Size

This is a Phase I, dose-escalation study. The sample size is based on the feasibility to assess safety. No statistical analysis of efficacy is planned.

9.2 Population

Statistical analysis will be based on an Intent-to-Treat design, but subjects must receive at least one dose of study drug and have at least one post-dose assessment.

9.3 Statistical Analysis

Safety and Tolerability:

The incidence and nature of adverse events will be reported in tabulated format. Adverse events will be described according to severity and to its relationship with the study drug. Serious adverse events and adverse events leading to treatment discontinuation will be listed.

Descriptive statistics (N, mean, median, SD, minimum and maximum values, where applicable) of safety laboratory parameters infection tests and tumor markers will be reported. Abnormalities will be summarized for low and high values.

Retinal fundoscopy results per treatment group will be reported as change from baseline and subsequent evaluation at day 365.

Efficacy:

Descriptive statistics (N, mean, median, SD, minimum and maximum values) of vascular assessments (ABI, TBI, Wave Form Analysis), TcPO₂, High Resolution MRA, VAS for pain, analgesic use, and ulcer size will be reported. Frequency counts for analgesics use by dose cohort will be reported.

Pharmacokinetics:

Descriptive statistics (N, mean, median, SD, minimum and maximum values, where applicable) of VM202 DNA levels will be reported.

Pharmacodynamics:

Descriptive statistics (N, mean, median, SD, minimum and maximum values, where applicable) of endothelial progenitor cell assay levels, anti-HGF antibody levels and serum HGF levels will be reported.

Change in endothelial progenitor cell levels from Baseline will be described for each treatment dose at each selected time point.

9.4 Data Safety Monitoring Committee

A Data Safety Monitoring Committee will review all safety data available 30 days after the first subject in each cohort is dosed and subsequent to day 15 dosing of the other 2 subjects in the same cohort. The committee will operate via Guidance Document and will have pre-specified stopping rules. The committee will review all safety data including severity, relationship to study drug, action taken with study drug and outcome. Study drug administration for the next cohort cannot begin until the committee reviews all of the data and reports its findings to ViroMed or their designee. There will also be continuing review of safety events after the Day 59 visit for all subjects at defined intervals until all subjects have completed the 6 month and 12 month follow-up visit (Day 365).

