After the first subject in each cohort completes day 30 (\pm 2 days), subsequent to day 15 dosing of the other 2 subjects in the same cohort, an interim safety evaluation will be performed with the submission of safety data to the Data Safety Monitoring Committee (DSMC). If the DSMC recommends continuing the study, the next dose cohort will be treated. This process will be repeated between the second and third dose cohort and between the third and fourth dose cohort. All 4 dose cohorts will be followed for one year from the time of the first dose of study drug administration. If a dose limiting toxicity is observed in one subject in any dose group, three additional subjects will be added to the dose cohort in which the toxicity was observed. If no additional DLTs are observed in the 6 subjects in this dose level, it will be considered the Maximum Tolerated Dose (MTD). If a DLT occurs in 2/6 subjects, then the preceding dose level will be considered the MTD.

Structure: Single center

Sample Size: Approximately 12-15 subjects

Study Population: Subjects selected for this study will have critical limb ischemia

that has not responded to standard therapy with symptoms

including pain at rest, and/or ischemic ulcers.

Study Assessments: The following assessments will be performed at screening and / or at designated time points throughout the study:

• Informed Consent

- Physical Exam
- Vital Signs
- Pregnancy Test
- Photograph and measurement of ulcer
- Mammogram
- Collection of concomitant medications
- Collection of medical history
- Assessment of CLI
- Collection of adverse events
- Ankle Brachial Index (ABI)
- Toe Brachial Index (TBI)

- Wave Form Analysis
- Transcutaneous Oxygen Pressure Assessment (TcPO₂)
- High resolution MRA
- Visual Analog Scale (VAS) for pain
- Analgesic usage
- Safety Laboratory Testing (Hematology, Chemistry, Urinalysis)
- Retinal fundoscopy
- 12-lead ECG
- Tumor marker testing (Alpha feto-protein, CEA, PSA [males only], CA19-9 & CA125)
- Infection testing (HIV, Hepatitis B, CMV, HTLV, VDRL)
- HGF levels
- Anti-HGF antibody levels
- VM202 DNA levels
- Endothelial progenitor cell assay
- Chest X-ray or CT scan of the chest (if the subject has a previous history of tobacco use, a CT scan will be performed instead of the chest X-ray)

Rationale:

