4.6 Duration

Each subject will be screened up to 30 days prior to receiving the first dose of study drug. Following screening, subjects will receive study drug on Day 1 and Day 15 and will be followed up until Day 365 post first dose of study medication. There will be safety evaluations that will begin 30 days after the first dose of study drug (Day 30) for all cohorts. Safety evaluations to encompass 30 days post the first dose of the first subject and subsequent to day 15 dosing of the other subjects in the same cohort will be completed for each cohort and will be evaluated by the DSMC prior to dose escalation to the next cohort. This 30-day window will include a 2-week safety evaluation following each dose at Day 1 and 15. The study will take approximately 30 months to complete. The individual subject enrollment will be approximately 12 months.

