6.2.4 Day 15 (± 3 days) Second Study Dose Administration

The second dose of study drug will be administered at Day 15 (\pm 3 days). Prior to the administration of the study agent, the following will be performed:

- Physical exam
- Vital signs (immediately after study drug administration and at 15, 30, and 60 minutes post-dose)
- Photograph and measurement of ulcer
- Urine Pregnancy test (females of childbearing potential)
- Clinical laboratory tests
- Tumor markers
- Serum HGF level

- anti-HGF antibodies
- TcPO₂
- Hemodynamic assessment
- Pain VAS
- Analgesic use
- Concomitant medications
- Adverse events

The study drug will be administered in the same manner and in the same dose as performed on Day 1. Following study drug administration, the following evaluations will be performed:

- Vital signs
- Injection site reaction assessment
- Endothelial progenitor cell assay
- Adverse events
- 6.2.5 Day 16 (post 2nd dosing)

The following procedures will be performed at the Day 16 visit:

- Vital signs
- Adverse events
- Clinical laboratory tests
- Analgesic use
- Injection site reaction assessment
- Concomitant medications
- 6.2.6 Day 21 (\pm 3 days)

The following procedures will be performed at the Day 21 (+ 3 days) visit

- Vital signs
- Serum HGF
- VM202 DNA levels
- Injection site reaction assessment
- Analgesic use
- Concomitant medications
- Adverse events
- 6.2.7 Day 28 (\pm 3 days)

The following evaluations will be performed at Day 28 (\pm 3 days):

- Physical exam
- Vital signs
- Photograph and measurement of ulcer
- Clinical laboratory tests
- Hemodynamic assessments (ABI, TBI, Wave Form)
- Pain VAS
- TcPO₂
- Endothelial progenitor cell assay
- Analgesic use
- Injection site reaction assessment
- Concomitant medications
- Adverse events

After all subjects in Cohort I have completed the Day 28 visit, enrollment will be temporarily suspended until the DSMC has reviewed all of the safety data for all subjects. If the DSMC recommends that the trial continue, enrollment in Cohort II will commence and all of the procedures from Day -30 through Day 28 will be repeated for Cohort II.

After all subjects in Cohort II have completed the Day 28 visit, enrollment will be temporarily suspended until the DSMC has reviewed all of the safety data for all subjects. If the DSMC recommends that the trial continue, enrollment in Cohort III will commence and all of the procedures from Day -30 through Day 28 will be repeated for Cohort III.

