After the first subjects in Cohort III have completed the Day 28 visit and subsequent to the dosing of the other subjects in the same cohort, enrollment will be temporarily suspended until the DSMC has reviewed all of the safety data for all subjects. If the DSMC recommends that the trial continue, enrollment in Cohort IV will commence and all of the procedures from Day -30 through Day 28 will be repeated for Cohort IV.

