7.1.9 Dose Limiting Toxicity (DLT)

Dose limiting toxicity will be defined as the occurrence of any of the following:

- Acute anaphylaxis including erythema, hives, wheals, wheezing, stridor or respiratory distress
- Temperature >102°F with negative blood cultures within 24 hours of study drug administration
- Evidence for active tissue necrosis at the injection site within two weeks of study drug administration

Dose limiting toxicities will be recorded on the CRF. In the event of a DLT at any dose, 3 additional subjects will be added to the dose cohort in which the toxicity was observed. If no additional DLTs are observed in the 6 subjects in this dose level, it will be considered the Maximum Tolerated Dose (MTD). If a DLT occurs in 2/6 patients, then the preceding dose level will be considered the MTD.

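### The escalation-review triggers conflict, none holds the next cohort until the two-week necrosis window after dose 2 has closed, and the fever DLT has no scheduled temperature reading

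*Protocol*

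**What the plan says.** **Review triggers.** The Synopsis starts the review "After the first subject in each cohort completes day 30" (±2 days), once the other two subjects have had the Day 15 dose. Section 9.4 says 30 days "after the first subject in each cohort is dosed and subsequent to day 15 dosing of the other 2 subjects". Section 4.6 has the same rule, places "safety evaluations that will begin 30 days after the first dose of study drug (Day 30) for all cohorts", and adds: "This 30-day window will include a 2-week safety evaluation following each dose at Day 1 and 15".

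Section 6.2.7 differs by cohort. For the first it reads "After all subjects in Cohort I have completed the Day 28 visit, enrollment will be temporarily suspended", with the same rule for Cohort II. For the step to Cohort IV it reads "After the first subjects in Cohort III have completed the Day 28 visit and subsequent to the dosing of the other subjects", without naming the dose. SAP section 3 has all subjects completing Day 30 ±2, repeated between later cohorts.

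**DLT definitions.** Section 7.1.9 lists "Evidence for active tissue necrosis at the injection site within two weeks of study drug administration". Section 6.2.4 states "The second dose of study drug will be administered at Day 15", with a tolerance of ±3 days. Section 7.1.9 also lists a temperature above 102°F within 24 hours of dosing with negative blood cultures. The vital-signs row of Table 4-1 names heart rate, blood pressure and respiration.

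**Gate to the next cohort.** Section 6.1.1 bars enrolment into a later cohort until the DSMC has reviewed the data and given written notice. It sets no minimum time since dose 2. Screening (6.2.1) may last up to 30 days and has no minimum.

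**The concern.** The 3+3 rule escalates, expands or stops on the DLT count in 3 or 6 subjects. A necrosis that appears after the review is not in the count the DSMC acts on. Under 9.4 as written, two of the three subjects can be reviewed with their entire post-dose-2 window still ahead. The step most exposed is Cohort III to IV, where the amount per administration doubles from 4 mg to 8 mg (6.1.1).

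Appendix E shows how the gap arose. Version 2 lengthened the necrosis window from 72 hours to two weeks and added the 4.6 sentence about two weeks after each dose. Version 5 moved the trigger to the first subject and left that sentence in place. Section 4.6 now promises follow-up that its own trigger does not secure for the other two subjects.

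The fever criterion has a related weakness: it feeds the same count, but no visit is scheduled to measure it.

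**Working it through.** **Inputs.** Necrosis window: 14 days (7.1.9). Dose 2: Day 15 ±3, so Day 18 at the latest (6.2.4, Table 4-1). Day 28 visit: ±3 (Table 4-1). Day 30 review: ±2 in the Synopsis and SAP section 3; no tolerance in 9.4. Section 4.6 equates 30 days after the first dose with Day 30.

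**The plan's own statement.** Dose 2 on Day 15 plus 14 days is Day 29, which lies inside Day 30. The 4.6 sentence is therefore right for a first subject treated exactly on schedule.

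**Days observed after dose 2 at the earliest permitted review** = trigger day − dose 2 day. Minimum = earliest trigger day − 18. Shortfall = 14 − minimum.

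| Trigger | Nominal | Minimum | Largest shortfall |
|---|---|---|---|
| 9.4, first subject | 30−15 = 15 | 30−18 = 12 | 2 |
| Synopsis, first subject | 30−15 = 15 | 28−18 = 10 | 4 |
| 9.4, 4.6 and Synopsis, other two | none set | 0 | 14 |
| 6.2.7, Cohorts I and II, all subjects | 28−15 = 13 | 25−18 = 7 | 7 |
| 6.2.7, Cohort III, first subject(s) | 28−15 = 13 | 25−18 = 7 | 7 |
| 6.2.7, Cohort III, others (if dose 2 is meant) | none set | 0 | 14 |
| SAP section 3, all subjects | 30−15 = 15 | 28−18 = 10 | 4 |

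The Day 28 rule is one day short (14 − 13) even on the nominal schedule. Of the permitted pairings of visit day and dose 2 day, 21 of 49 reach 14 days under Day 28 ±3 and 25 of 35 under Day 30 ±2. These are counts of pairings, not probabilities.

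**Figure 4-1, Cohort III to IV.** Dose 2 is on Day 153, the review on Days 168–175, Cohort IV screening from Day 177 and its first dose on Day 207.

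- Dose 2 to review: 168−153 = 15 to 175−153 = 22 days.
- Dose 2 to Cohort IV dosing: 207−153 = 54 days.
- Staggered enrolment with a dose 2 as late as Day 175: the window closes on Day 175+14 = 189, after the review but 207−189 = 18 days before Cohort IV dosing.
- In that case Cohort IV is dosed inside an open window only if screening takes less than 189−177 = 12 days.

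**Effect on the count (illustration).** Assume a per-subject DLT risk *p*, of which a share *s* falls after dose 2 and is unseen in the other two subjects. The first subject is fully observed. The documents give neither *p* nor *s*.

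- Full follow-up: P(at least 1 DLT seen) = 1−(1−p)³.
- Early review: 1−(1−p)(1−p(1−s))².
- p = 0.20, s = 0.5: 1−0.8³ = 48.8%, against 1−0.8×0.9² = 35.2%. With s from 0.25 to 0.75, the second figure runs from 42.2% to 27.8%.
- At s = 0.5, the fall is from 27.1% to 18.8% for p = 0.10 and from 69.9% to 53.3% for p = 0.33.

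This is the extreme that 9.4 permits, with both other subjects reviewed right after dose 2.

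**Fever.** After dose 1 the subject is observed for at least 60 minutes. The next visit is Day 8 ±2, at the earliest Day 6, which is 5 days after dosing. After dose 2 the next visit is Day 16. Neither the Table 4-1 vital-signs row nor any visit list names temperature. Serum sickness (low-grade fever within 72 hours, 7.1.8) and the drug-fever grades split at 38°C (7.1.6) have the same gap, although they are not DLTs.

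**The case against.** The strongest reply is that harm needs several unlikely things together. On Figure 4-1, Cohort IV is dosed 54 days after Cohort III's dose 2. An overlap needs late staggered dosing and screening completed in under 12 days, and screening includes MRA, an ophthalmologist's examination, chest imaging and laboratory tests. This stands as a statement of likelihood. It does not supply a rule: the interval comes from a maximum screening period, and some earlier test results are accepted (5.1, 7.1.4).

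Early review was also deliberate. Appendix E justifies it by the safety seen in the first two cohorts, which explains the split in 6.2.7 and makes the Cohort I and II shortfalls less pressing. The unnamed dosing in 6.2.7 is reasonably read as dose 2, since the Synopsis, 4.6 and 9.4 all say so. The SAP text is a version-control defect, not an operating rule. All of this is fair. It narrows the exposure to Cohort III to IV, but those first two cohorts did not receive Cohort III's dose.

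Late DLTs are not ignored: 7.1.9 would still expand the cohort, and injection sites are checked on Days 15 (post-dose), 16, 21, 28 and 59. Detection, however, does not delay the next cohort's first dose. The DSMC Guidance Document cited in 9.4 may deal with open windows, but it is not among the documents.

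On fever, subjects are told to call at once and seek evaluation, and further dosing waits for a DLT determination or the treating physician's direction (6.2.2). Day 16 gives a next-day visit after dose 2. The CRF may hold a temperature field. These reduce the gap, but the protocol still schedules no reading.

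**Conclusion.** The point holds and should be fixed. The current texts give different review triggers, and none ensures that the two-week necrosis window after the actual second dose is complete. Under 9.4 the shortfall can be the full 14 days for two of three subjects. For the first subject it is at most 2 days under 9.4 and 4 under the Synopsis; under 6.2.7 it is 1 day nominally and 7 at most.

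These are shortfalls at the review. An open window at the next cohort's first dose is improbable on the planned calendar, but no written rule prevents it. The day counts rest only on the stated visit windows. The detection figures rest on assumed risks and show direction and order of size, not an estimate.

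The fever DLT depends on a subject calling in and on adverse-event questioning. That conclusion assumes that neither the CRF nor the DSMC Guidance Document adds a temperature reading.

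**What to change.** 1. State one review trigger in the Synopsis, 4.6, 6.2.7 and 9.4, name the dose, bring SAP section 3 into line, and correct the 4.6 sentence on two weeks after each dose.
2. If early review is kept, add that no subject in the next cohort is dosed until every subject in the prior cohort is at least 14 days past the actual dose 2. Add a column to the DSMC table showing which windows are still open.
3. Add temperature to the vital-signs row of Table 4-1, including the post-dose and Day 16 readings, with a home reading or telephone call covering the 24 hours after each dose.

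The cost is wording changes, one table column, and a thermometer reading and a call per dose. The hold adds no delay on the Figure 4-1 calendar and at most about two weeks at an escalation, mainly Cohort III to IV.
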